
 To investigate the effect of daprodustat and epoetin alfa on vasoactive mediators of blood pressure 	
 Plasma concentrations and derived parameters including C_{max}, t_{max}, t_{1/2} and AUC(0-24) as appropriate (to include erythropoietin, endothelin-1, nitric oxide, asymmetric dimethylarginine, renin, angiotensin-II and metabolites, and noradrenalin)

 To summarize the effect of daprodustat and epoetin alfa on SBP after Acute Challenge 1 and Acute Challenge 2 	
 AUEC of SBP as measured by ABPM over 24-hr post-dosing

 To compare the effect of daprodustat to epoetin alfa on SBP after 8 weeks of Hgb maintenance therapy 	
 Change from Day 1 pre-dose SBP to Day 57 pre-dose

 To compare the effect of daprodustat to epoetin alfa on SBP at C_{max} of each study treatment, as measured by ABPM 	
 Change in SBP from pre-dose on Day 1 to C_{max} of the study treatment on Day 1 Change in SBP from pre-dose on Day 1 to C_{max} of the study treatment on Day 57 Change in SBP from pre-dose on Day 57 to C_{max} of the study treatment on Day 57

 To compare the effect of daprodustat to epoetin alfa on SBP at C_{max} of the erythropoietin level, as measured by ABPM 	
 Change in SBP from pre-dose on Day 1 to C_{max} of erythropoietin on Day 1 Change in SBP from pre-dose on Day 1 to C_{max} of erythropoietin on Day 57 Change in SBP from pre-dose on Day 57 to C_{max} of erythropoietin on Day 57

[figure not shown]

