## 5.2. Baseline Definitions and Derivations

### 5.2.1. Baseline Definitions

For all endpoints the baseline value will be the latest non-missing pre-dose assessment before Acute Challenge 1 as detailed in the following table. Pre-dose values following Acute Challenge 1 following the maintenance therapy will not be used as baseline.

Parameter	Study Assessments Considered As Baseline			Baseline Used in Data Display
	Screening	Week -2	Day 1 (Pre-Dose)	
Pre-Acute Challenge 1				
ABPM Parameters			X	Post-HD/Pre-Acute Challenge 1
Vital signs (SBP, DBP and pulse rate)	X	X	X (post-HD)	Post-HD and Pre-Acute Challenge 1
Laboratory data	X		X	Day 1(Pre-dose)
ECG	X		X	Day 1(Pre-dose)
Biomarkers			X	Day 1(Pre-dose)
NOTES: Unless otherwise stated, the mean of replicate assessments at any given time point will be used as the value for that time point.				

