### 11.3. Exploratory Pharmacodynamic and Biomarker Analyses

#### 11.3.1. Endpoint / Variables

Exploratory Objectives	Exploratory Endpoints

 
To investigate the effect of daprodustat and epoetin alfa on vasoactive mediators of blood pressure
 
	
 
Plasma concentrations and derived parameters including Cmax, tmax, and AUC(0-24) as appropriate (to include erythropoietin, endothelin-1, nitric oxide, asymmetric dimethylarginine, renin, angiotensin-II and metabolites, and noradrenalin)
 

CONFIDENTIAL

205665

Exploratory Objectives	Exploratory Endpoints

 
To summarize the effect of daprodustat and epoetin alfa on SBP after Acute Challenge 1 and Acute Challenge 2
 
	
 
AUEC of SBP as measured by ABPM over 24-hr post-dosing
 

 
To compare the effect of daprodustat to epoetin alfa on SBP after 8 weeks of Hgb maintenance therapy
 
	
 
Change from Day 1 pre-dose SBP to Day 57 pre-dose
 

 
To compare the effect of daprodustat to epoetin alfa on SBP at Cmax of the study treatment
 
	
 
Change in SBP from pre-dose on Day 1 to Cmax of the study treatment on Day 1, as measured by ABPM
 
Change in SBP from pre-dose on Day 1 to Cmax of the study treatment on Day 57, as measured by ABPM
 
Change in SBP from pre-dose on Day 57 to Cmax of the study treatment on Day 57, as measured by ABPM
 

 
To compare the effect of daprodustat to epoetin alfa on SBP at Cmax of the erythropoietin level
 
	
 
Change in SBP from pre-dose on Day 1 to Cmax of erythropoietin on Day 1, as measured by ABPM
 
Change in SBP from pre-dose on Day 1 to Cmax of erythropoietin on Day 57, as measured by ABPM
 
Change in SBP from pre-dose on Day 57 to Cmax of erythropoietin on Day 57, as measured by ABPM
 

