### 11.3.1.1. Statistical Methodology Specification

Endpoint / Variables

 
Cmax, tmax, and AUC(0-24) for erythropoietin, endothelin-1, nitric oxide, asymmetric dimethylarginine, renin, angiotensin-II and metabolites, and noradrenalin
 
AUEC of SBP, comparing Day 57 vs Day 1
 
Change in pre-dose SBP from Day 1 to Day 57
 
Change in SBP from pre-dose on Day 1 to Cmax of the study treatment on Day 1, as measured by ABPM
 
Change in SBP from pre-dose on Day 57 to Cmax of the study treatment on Day 1, as measured by ABPM
 
Change in SBP from pre-dose on Day 57 to Cmax of the study treatment on Day 57, as measured by ABPM
 
Change in SBP from pre-dose on Day 1 to Cmax of erythropoietin on Day 1, as measured by ABPM
 
Change in SBP from pre-dose on Day 57 to Cmax of erythropoietin on Day 1, as measured by ABPM
 
Change in SBP from pre-dose on Day 57 to Cmax of erythropoietin on Day 57, as measured by ABPM
 

Overview of exploratory endpoints

 
For each acute challenge, the concentration of erythropoietin, endothelin-1, nitric oxide, asymmetric dimethylarginine, renin, angiotensin-II and metabolites, and noradrenalin will be summarized by treatment group at each timepoint. Descriptive statistics (n, arithmetic mean, standard deviation, minimum, median, maximum) will be calculated for all biomarkers endpoints by regimen. In addition, for AUC, Cmax, tmax, baseline adjusted AUC and baseline adjusted Cmax; geometric means and geometric CVs (CVb(%)) will be calculated for each regimen. Geometric mean and geometric CV% will not be calculated for tmax. Line graphs of this information will be provided by treatment group for
 

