**CONFIDENTIAL**

205665

each acute challenge. Cmax, tmax, AUC(0-24), baseline adjusted AUC and baseline adjusted Cmax will all be summarized by treatment arm and for each acute challenge day.
 
 
• Change in AUEC of SBP from Day 57 to Day 1 for each treatment arm will be summarized in a table.
 
• The difference in SBP between pre-dose in Acute Challenge 1 and pre-dose in Acute Challenge 2 will be summarized by treatment group. Similar summaries of DBP, MAP, and HR will be performed.
 
• For each acute challenge, change from pre-challenge in SBP, DBP, MAP, and HR will be summarized by treatment group at each timepoint. In addition, for each acute challenge, SBP, DBP, MAP, and HR will be summarized by treatment group at each timepoint. Line graphs of this information will be provided by treatment group for each acute challenge.
 
• For the following endpoints, an ANCOVA model will be used with terms for baseline SBP, treatment, and prior ESA dose (low/high): 
 
○ Change in SBP from pre-dose on Day 1 to Cmax of the study treatment on Day 1, as measured by ABPM
 
○ Change in SBP from pre-dose on Day 57 to Cmax of the study treatment on Day 1, as measured by ABPM
 
○ Change in SBP from pre-dose on Day 57 to Cmax of the study treatment on Day 57, as measured by ABPM
 
○ Change in SBP from pre-dose on Day 1 to Cmax of erythropoietin on Day 1, as measured by ABPM
 
○ Change in SBP from pre-dose on Day 57 to Cmax of erythropoietin on Day 1, as measured by ABPM
 
○ Change in SBP from pre-dose on Day 57 to Cmax of erythropoietin on Day 57, as measured by ABPM
 
 
 

Model Checking & Diagnostics
 
 
• Distributional assumptions underlying the statistical analyses will be assessed by visual inspection of residual plots. Normality will be examined by normal probability plots, while homogeneity of variance will be assessed by plotting the residuals against the predicted values for the model. If assumptions are grossly violated, alternative analyses will be considered.
 

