
 
• For exploratory endpoints utilizing ANCOVA models:               
 
○ Baseline SBP data point will come from the SBP/DBP/HR/MAP reading recorded from the ABPM data. The zero time, first recorded measurement from the ABPM device, will be used as the post HD pre acute challenge variable as per the guidelines under ABPM data.                   
 
▪ If the data is missing from the ABPM data, the eCRF vital signs data will be used                       
 
• Post-dialysis measurement will be used
 
 
 
▪ If MAP variable is needed from eCRF, MAP will be calculated the following way:
 
▪ <math>MAP = (SBP + 2(DBP)) / 3</math>
 
 
 
○ Change from baseline will be defined as average of the BP from ABPM device, within <math>\pm 20</math> min from tmax, minus the baseline SBP data point.                   
 
▪ Discrete timepoints will be used
 
▪ If no ABPM data is available with the <math>\pm 20</math> min window, then the calculated average will be marked as “.” to indicate missing since no ABPM data is available within that window.
 
 
 
○ If repeat day 57 data is available, then the Cmax data will be based on the non-repeat visit and the ABPM data will be based on the repeated visit.
 
○ If more than one tmax is listed for a given cmax, only the first tmax will be used.
 
 
 
• For Daprodustat subjects, the tmax from treatment and the tmax from epoetin alfa data will be used
 
• For rEPO subjects, the tmax from epoetin alfa will be used for both endpoints analysing tmax of ABPM data.
 
					
Plot of ABPM Data					

 
• Hourly average of each of the four ABPM measurements (SBP, DBP, MAP, and HR) for AC1 and AC2 will be generated for each subject               
 
○ Hourly averages defined as follows:
 
 
 
					
Hour	Measurement 1	Measurement 2	Measurement 3	Measurement 4	Average
0-1	121	115	122	120	$(121+115+122+120)/4 = 119.5$
...					
5-6	121	115	122	Missing	$(121+115+122)/3 = 119.3$
6-7	121	115	122	No data possible	$(121+115+122)/3 = 119.3$
...					
23-24	120	121	missing	No data possible	$(120+121)/2=120.5$

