**CONFIDENTIAL**

205665

Pharmacodynamic and Biomarker: Tables					
No.	Population	IDSL / Example Shell	Title	Programming Notes	Deliverable
4.18.	ITT	PDT4	Summary of Analysis of AUEC DBP over 24hr post-AC2		DR, SAC
4.19.	ITT	PDT4	Summary of Analysis of AUEC MAP over 24hr post-AC2		DR, SAC
4.20.	ITT	PDT4	Summary of Analysis of AUEC HR over 24hr post-AC2		DR, SAC
4.21.	ITT	PDT5	Summary of change from pre-dose SBP	At each timepoint on day 1 and day 57 by treatment	DR, SAC
4.22.	ITT	PDT5	Summary of change from pre-dose DBP	At each timepoint on day 1 and day 57 by treatment	DR, SAC
4.23.	ITT	PDT5	Summary of change from pre-dose MAP	At each timepoint on day 1 and day 57 by treatment	DR, SAC
4.24.	ITT	PDT5	Summary of change from pre-dose HR	At each timepoint on day 1 and day 57 by treatment	DR, SAC
Exploratory Endpoints					
4.25.	ITT	PDT6	Summary of Change from Day 1 AUEC of 24hr SBP to Day 57 AUEC of 24hr SBP		DR, SAC
4.26.	ITT	PDT7	Summary of change from Day 1 pre-dose SBP to Day 57 pre-dose		DR, SAC
4.27.	ITT	PDT3	Summary of Analysis of change in SBP from pre-dose on Day 1 to Cmax of the study treatment on Day 1, as measured by ABPM		DR, SAC
4.28.	ITT	PDT3	Summary of Analysis of change in SBP from pre-dose on Day 57 to Cmax of the study treatment on Day 1, as measured by ABPM		DR, SAC
4.29.	ITT	PDT3	Summary of Analysis of change in SBP from pre-dose on Day 57 to Cmax of the study treatment on Day 57, as measured by ABPM		DR, SAC

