**CONFIDENTIAL**

205665

Pharmacodynamic and Biomarker: Tables					
No.	Population	IDSL / Example Shell	Title	Programming Notes	Deliverable
4.30.	ITT	PDT3	Summary of Analysis of change in SBP from pre-dose on Day 1 to Cmax of erythropoietin on Day 1, as measured by ABPM		DR, SAC
4.31.	ITT	PDT3	Summary of Analysis of change in SBP from pre-dose on Day 57 to Cmax of erythropoietin on Day 1, as measured by ABPM		DR, SAC
4.32.	ITT	PDT3	Summary of Analysis of change in SBP from pre-dose on Day 57 to Cmax of erythropoietin on Day 57, as measured by ABPM		DR, SAC
Biomarker Concentration Table, Exploratory Endpoints					
4.33.	ITT	PK01	Summary of Biomarker Plasma Concentration-Time Data		DR, SAC
Biomarker Derived Parameters, Exploratory Endpoints					
4.34.	ITT	PK06	Summary of Derived Biomarker Plasma Parameters (Non-Transformed)	Parameters with units Include baseline adjusted AUC and CMAX	DR, SAC
4.35.	ITT	PK06	Summary of Derived Biomarker Plasma Parameters (Ln-Transformed)	Parameters with units Include baseline adjusted AUC and CMAX	DR, SAC
Sensitivity Analyses					
4.36.	PP	PDT3	Summary of Analysis of Average 6hr ABPM SBP post-AC2, Per Protocol	Use PP population if at least 10% of the ITT population is excluded from PP population	DR, SAC

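### SAP 11.3.1.1 and Tables 4.28 and 4.31 reverse the days of two exploratory SBP-at-Cmax endpoints, so the defined Day 1 pre-dose to Day 57 Cmax comparison has no planned analysis

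*SAP*

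**What the plan says.** Protocol section 3 and the synopsis list three SBP-at-Cmax endpoints for study treatment and three for erythropoietin. The second in each set crosses the two challenge days; for study treatment it reads "Change in SBP from pre-dose on Day 1 to C_{max} of the study treatment on Day 57". SAP 2.2 and SAP 11.3.1 agree, the latter with "Change in SBP from pre-dose on Day 1 to Cmax of the study treatment on Day 57, as measured by ABPM". The erythropoietin versions follow the same pattern in all four places.

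SAP 11.3.1.1, which turns these endpoints into models, reverses the days. Its variable list and its ANCOVA list both give "Change in SBP from pre-dose on Day 57 to Cmax of the study treatment on Day 1, as measured by ABPM", and for erythropoietin "Change in SBP from pre-dose on Day 57 to Cmax of erythropoietin on Day 1, as measured by ABPM". In SAP 14.12.8, Table 4.28 is titled as an analysis of "change in SBP from pre-dose on Day 57 to Cmax of the study treatment on Day 1, as measured by ABPM" and Table 4.31 as an analysis of "change in SBP from pre-dose on Day 57 to Cmax of erythropoietin on Day 1, as measured by ABPM".

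Three other parts of the SAP bear on the baseline day:

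- SAP 5.2.1 takes baseline, for all endpoints, from the last pre-dose value before Acute Challenge 1 and adds: "Pre-dose values following Acute Challenge 1 following the maintenance therapy will not be used as baseline".
- SAP 14.6.6 derives the change as the average ABPM reading within 20 minutes either side of tmax "minus the baseline SBP data point", without naming a day.
- The ANCOVA list in 11.3.1.1 adjusts for baseline SBP, also without naming a day.

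**The concern.** The four places that define the endpoints agree with one another, and the three places that tell the programmer what to run say something else. The reversed version starts from a reading taken after eight weeks of randomized treatment and ends at one taken on the first day of treatment. As a measure of change it has no evident interpretation.

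The cross-day pair is the only one of the three in each set that combines the eight-week shift in pre-dose SBP with the acute response after maintenance. That between-arm comparison could be lost, and a table with a different content could be reported in its place.

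**Working it through.** **Location of each version**

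| Place | Direction | Statements |
|---|---|---|
| Protocol synopsis | Day 1 pre-dose to Day 57 Cmax | 2 |
| Protocol 3 | Day 1 pre-dose to Day 57 Cmax | 2 |
| SAP 2.2 | Day 1 pre-dose to Day 57 Cmax | 2 |
| SAP 11.3.1 | Day 1 pre-dose to Day 57 Cmax | 2 |
| SAP 11.3.1.1, variable list | Day 57 pre-dose to Day 1 Cmax | 2 |
| SAP 11.3.1.1, ANCOVA list | Day 57 pre-dose to Day 1 Cmax | 2 |
| SAP 14.12.8, Tables 4.28 and 4.31 | Day 57 pre-dose to Day 1 Cmax | 2 |

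That is 8 statements one way and 6 the other. SAP Table 1, which records departures from the protocol, has no entry for these endpoints.

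**The two quantities.** Let P1 and P57 be pre-dose SBP, and C1 and C57 be SBP at Cmax, on Days 1 and 57.

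- Defined: C57 − P1 = (C57 − P57) + (P57 − P1)
- Written in 11.3.1.1: C1 − P57 = (C1 − P1) − (P57 − P1)

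They have 0 of 2 measurements in common. The written form replaces the Day 57 challenge response with the Day 1 response and enters the eight-week pre-dose change with the opposite sign.

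**What the ANCOVA would estimate.** When the same baseline is both subtracted and used as covariate, the treatment coefficient is the one obtained by modelling the end value on that baseline:

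- Defined endpoint with P1: the arm difference in C57 adjusted for P1.
- Written endpoint with P57: the arm difference in C1 adjusted for P57. No Day 57 challenge response enters, and the covariate is post-randomization. SAP 5.4.1 itself says that the Day 57 pre-challenge value is not a true pre-treatment covariate.

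If a programmer instead kept Cmax on Day 1 as written but applied the SAP 5.2.1 baseline, the result would be C1 − P1. That is already the content of Table 4.27 or 4.30. Neither route gives C57 − P1.

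**Whether another table supplies it**

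- Tables 4.27 and 4.30 are within Day 1.
- Tables 4.29 and 4.32 are within Day 57.
- Table 4.21 gives change from pre-dose by timepoint on each day.
- Table 4.26 summarizes P57 − P1 only.

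From subject data, C57 − P1 can be rebuilt as the Table 4.26 quantity plus the Table 4.29 or 4.32 quantity. No planned model does this, so the treatment difference, 95% CI and p-value that 11.3.1.1 promises for every ANCOVA would not exist for the two defined endpoints.

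**The case against.** The best case for leaving this alone is that it is a visible drafting slip. SAP 11.3.1 states the endpoint correctly just before 11.3.1.1 reverses it. The general baseline rule in 5.2.1 and the change formula in 5.2.2 (post-dose value minus baseline) both point to Day 1 pre-dose. An outcome that precedes its own baseline by eight weeks is likely to be queried before anyone runs it. The mock shells are separate documents and may already be right. The endpoints are exploratory with no Type I error control, and the data are kept either way.

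Most of this is fair. It limits the stakes and makes the loss conditional on programming the SAP as written. It also supports Day 1 as the intended baseline.

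It does not remove the contradiction. The reversed wording is in both operative lists and in the titles of two tables scheduled for the dry run and final delivery. The baseline rule cannot be applied mechanically either, because the Day 57-to-Day 57 endpoints depart from it. Section 5.2.2 allows otherwise-specified exceptions, and the reversed text could claim the same allowance. Loose wording of direction does not explain it: the same section speaks of AUEC change from Day 57 to Day 1, but there a reversal alters only the sign. Here each day is attached to a different measurement.

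**Conclusion.** The concern holds. Two of the six SBP-at-Cmax ANCOVAs, and the two tables that report them, are specified for a quantity other than the one the protocol and the SAP's endpoint lists define, with no declared change. If the SAP is followed as written, the planned between-arm comparison for the two cross-day endpoints is not produced.

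The effect is confined to exploratory analyses. The primary and secondary analyses and the other four Cmax models (Tables 4.27, 4.29, 4.30 and 4.32) are not affected by the reversal. No error in mmHg can be stated. It would depend on the arm difference in the eight-week pre-dose shift, any change in the acute effect between the two days, and the covariate slope, and the documents give none of these. The conclusion assumes that programming follows 11.3.1.1 and the table titles; the shells and programs were not available to check.

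**What to change.** - In both lists of SAP 11.3.1.1 and in the titles of Tables 4.28 and 4.31, restore the change from pre-dose on Day 1 to Cmax on Day 57, for study treatment and for erythropoietin respectively.
- For these two models, use Day 1 pre-dose SBP both as the value subtracted and as the covariate.
- In SAP 14.6.6, state the baseline day for each of the six SBP-at-Cmax models.
- In SAP 5.2.1, note that the Day 57-to-Day 57 endpoints are an exception to the baseline rule.
- If the reversal was intended, declare it with a reason in SAP Table 1 and bring the endpoint lists into line.

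The cost is wording in two lists and two titles, plus the baseline statements. No new data are needed. The shells and programs should be checked against the corrected text; the documents do not show how much reprogramming that would take.

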## 12. PHARMACOKINETIC / PHARMACODYNAMIC ANALYSES

### 12.1. Primary Pharmacokinetic / Pharmacodynamic Analyses

There are no primary Pharmacokinetic / Pharmacodynamic Analyses, only exploratory. The primary objective is Pharmacodynamic, the average systolic blood pressure (SBP) over 6-hr post-dosing after 8 weeks, this is described in Section 11.

### 12.2. Secondary Pharmacokinetic / Pharmacodynamic Analyses

There are no secondary Pharmacokinetic / Pharmacodynamic Analyses, only exploratory. The primary objective is Pharmacodynamic, the average systolic blood pressure (SBP) over 6-hr post-dosing after 8 weeks, this is described in Section 11.

### 12.3. Exploratory Pharmacokinetic / Pharmacodynamic Analyses

#### 12.3.1. Endpoint / Variables

 
To investigate if an exposure-response relationship exists between daprodustat and BP
 
	
 
The daprodustat exposure (AUC) compared to the AUEC of SBP, DBP, MAP, and HR at Day 1 and Day 57
 

 
To investigate if an exposure-response relationship exists between daprodustat and biomarkers of interest
 
	
 
The daprodustat exposure (AUC) compared to the biomarker AUEC at Day 1 and Day 57. Biomarkers included erythropoietin, endothelin-1, nitric oxide, asymmetric dimethylarginine, renin, angiotensin-II (and metabolites), and noradrenalin.
 

#### 12.3.2. Summary Measure

To investigate if an exposure-response relationship exists between daprodustat and average systolic blood pressure (SBP), the daprodustat exposure (AUC) and SBP, DBP, MAP and HR AUEC from Days 1 and 57 will be plotted to determine if further modelling is required. Similar plot analyses (daprodustat AUC vs. biomarker AUEC on Days 1 and 57) will be explored to determine if a daprodustat exposure-response relationships exist with: erythropoietin, endothelin-1, nitric oxide, asymmetric dimethylarginine, renin, angiotensin-II (and metabolites), and noradrenalin to determine if further modelling is deemed necessary.

These figures will be created for Day 1 and Day 57 visits. The x-axis will be the AUC of Daprodustat for each subject and the y-axis will be the AUEC of either BP or biomarkers for that subject. The figures will be scatter plots.

#### 12.3.3. Population of Interest

The exploratory Pharmacokinetic / Pharmacodynamic Analyses will be based on the PK population, unless otherwise specified.

**12.3.4. Strategy for Intercurrent (Post-Randomization) Events**

Not required.

**12.3.5. Statistical Analyses / Methods**

Details of the planned displays are provided in [Appendix 12: List of Data Displays](#) and will be based on GSK Data Standards and statistical principles.

CONFIDENTIAL

205665

## 14. APPENDICES

### 14.1. Appendix 1: Protocol Deviation Management and Definitions for Per Protocol Population

#### 14.1.1. Exclusions from Per Protocol Population

A participant meeting any of the following criteria will be excluded from the Per Protocol population as detailed in the PDMP V5.0:

Number	Exclusion Description
01	Signed informed consent/assent not available on site
02	Wrong informed consent/assent version signed
03	Informed consent/assent not signed and/or dated by participant (parent/Legally Acceptable representative, if applicable)
04	Informed consent/assent not signed and/or dated by appropriate site staff.
05	Informed consent/assent not signed prior to any study procedure
06	Other informed consent/assent deviations
07	Meets Hgb stopping criteria
08	Receives a blood transfusion
09	Receives a kidney transplant
10	Becomes pregnant
11	Misses 2 consecutive dialysis sessions
12	Need for chronic use of prohibited medication
13	Myocardial infarction or acute coronary syndrome
14	Stroke or transient ischemic attack
15	New diagnosis of heart failure
16	Active chronic inflammatory disease that could impact erythropoiesis
17	Any new diagnosis of hematological disease
18	Active GI bleeding
19	Medication, excluded by the protocol, was administered*
20	Wrong study treatment or assignment administered
21	Assessment not properly performed*
22	Missed visit/phone contact*

